## **16.2** Secondary Endpoint Analyses

## **16.2.1 Cure rate by POC-CCA**

### Analysis set(s):

• Primary analyses will be based on the mITT and PP analysis sets.

### Clinical cure rate by POC-CCA:

CR by POC-CCA will be analysed in the same manner as CR by Kato-Katz as described above. In addition, estimates of cure rate will be presented graphically in the form of forest plots presenting means and 95% CIs of treatment groups and proportion of patients with each POC-CCA response (negative, positive 1+, positive 2+ and positive 3+) for the following time points:

- D-28 to D-1
- D2
- D8
- D14- D21

The proportion of CCA negative, 1+, 2+ and 3+ participants (colour-coded for category) will be plotted over time, for each of the cohorts. The same will be plotted for treatment types (Biltricide®, rac-PZQ and L-PZQ), instead of cohorts.

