7.1.4 Follow-up visit

Follow-up visits will take place as specified in APPENDIX II.

During the 3 days following their release from the hospital, subjects will be monitored by the nurses in the health areas and/or by the community agents of the different localities for potential adverse events. If an AE is observed, the latter need to inform the medical team in charge of the study for the necessary follow up.

At day 8 (+/- 1 day), urine samples will be collected for the POC-CCA test. If an AE related to liver function occurs before hospital discharge (within 24 hours after dosing), the subject will be further monitored by the study team in the villages and an additional blood sample will be collected at Day 8 for biochemistry evaluation.

At the End of Study visit (between day 14 and 21), subjects will be asked to provide stool and urine samples for Kato-Katz method and POC-CCA test. The following tests and information gathering will be also performed:

Vital signs in supine position including:

- Blood pressure (systolic and diastolic) to be assessed at least 5 minutes after resting
- Pulse rate to be assessed at least 5 minutes after resting
- Body temperature

Complete physical examination

If a subject withdraws prematurely from the trial, every effort will be made to undertake a final examination visit as soon as possible and perform all procedures of the End of Study visit.

Any ongoing medically relevant abnormal findings at the End of Study visit, including safety laboratory tests, will be followed up until resolution or stabilization (according to Section 7.4.1.6)

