8.5.1 General Considerations

Handling of subjects who drop out from the trial and missing data

For continuous endpoints, the imputation method of last observation carried forward will be used for the missing at the post-baseline measurement.

For binary endpoints, the imputation method of worst case will be used for the missing data at the post-baseline measurement.

The primary analysis will be based on mITT analysis population with missing imputations. All the observed cases will be analysed as sensitivity analysis.

Pharmacokinetic calculations

Not applicable..

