## 9 Changes to the Planned Analyses in the Clinical Trial Protocol

The statistical methods as described in the protocol were adopted.

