### **Overall clinical cure rate:**

Subjects cured of infection during the trial will be labelled as "responders". Responders will be defined as subjects with no parasite eggs (as determined by Kato-Katz method) in the End of Study

stool samples, 14-21 days after treatment, according to the eCRF page "Follow-up visit on D14-D21". Responders and non-responders will be coded as follows:

- For responders, *response* = 1
- For non-responders, response = 0

If the End of Study Kato-Katz egg count is missing, it will be imputed using the Last Observation Carried Forward (LOCF) approach. Subjects with missing data will be considered non-responders.

The proportion of responders in each cohort will be determined based on a binomial distribution. Exact 95% CIs will be calculated based on the Clopper-Pearson method. The PROC FREQ procedure in SAS will be used with the appropriate BINOMIAL and EXACT statements for point estimates and corresponding 95% CIs.

Point estimates and corresponding 95% CIs will be presented for cure rate, in terms of proportion of responders, by cohort. Response will be listed by cohort and subject. Estimates of cure rate will be presented graphically in the form of forest plots presenting means and 95% CIs.

Results will be presented for each analysis set.

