### Clinical cure rate by subgroup:

Again, analyses will be based on responders, which will be defined as was done in section 16.1.1 of this SAP. If the End of Study Kato-Katz egg count is missing, it will be imputed using the LOCF approach. Subgroup analyses of Part 1 and Part 2 of the study will be performed separately, by the following subgroups:

- Age category
- Gender
- Severity of infection
- Trial site (if applicable, i.e. more than one site)

Descriptive statistics of cure rates for each subgroup, individually and all in combination (four-way), will be estimated for each cohort using PROC FREQ.

Subgroup analysis will be performed utilising logistic regression to model clinical cure, i.e. *response* on gender, age category, severity of infection, day of assessment (e.g., Day 14-21), dose, formulation (ODT or not) and active pharmaceutical ingredient (L-PZQ or not [i.e. rac-PZQ]). The analysis will be repeated and presented separately for planned dose (mg/kg) *vs.* actual dose with respect to body weight (mg/kg) and actual dose in mg. Definitions and reference levels of subgroups are described in section 10.2.1 of this SAP. The PROC LOGISTIC procedure in SAS will be used with appropriate DESCENDING (to model on *response*=1) and PARAM=REF

(dummy coding for parameter estimates) statements to determine odds ratio point estimates and corresponding 95% Wald CIs.

To compliment PROC LOGISTIC results, the diagnostic plots using Pearson residuals will be produced [PLOTS(ONLY LABEL)=(INFLUENCE)].

Cure rate, in terms of proportion of responders, will be summarised by cohort (and by infection severity), and listed by cohort and subject. Estimates of cure rate will be presented graphically in the form of a forest plots presenting means and 95% CIs, by subgroup and cohort. For logistic regression results, odds ratio point estimates of model parameters and corresponding 95% CIs will be presented for each parameter, by cohort. Dose-response curves will be presented for the different active pharmaceutical ingredients (rac-PZQ/L-PZQ), separated by severity of infection, as well as pooled (all infections). Dose response curves will be generated for planned dose (in mg/kg), actual dose with respect to weight (in mg/kg) and actual dose in mg. These summary tables will be followed by the respective diagnostic plots.

Results will be presented for each analysis set.

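### POC-CCA cure inherits two missing-data rules, LOCF and missing-as-non-responder, that can conflict for this test; the SAP sets no order between them, and LOCF would depart from the protocol

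*SAP*

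**What the plan says.** SAP 16.2.1 defines the POC-CCA cure analysis by reference: "CR by POC-CCA will be analysed in the same manner as CR by Kato-Katz as described above". It sets no missing-data rule of its own.

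The section it refers to, SAP 16.1.1, puts two rules next to each other. The first is "If the End of Study Kato-Katz egg count is missing, it will be imputed using the Last Observation Carried Forward (LOCF) approach". The second is "Subjects with missing data will be considered non-responders". Neither is said to take precedence.

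SAP 16.1.2 (subgroup and logistic analyses) repeats the LOCF sentence without the non-responder sentence, but ties itself back to the main definition: "Again, analyses will be based on responders, which will be defined as was done in section 16.1.1 of this SAP".

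Protocol 8.5.1 separates the two kinds of endpoint. LOCF is for continuous endpoints. For the others, "For binary endpoints, the imputation method of worst case will be used for the missing data at the post-baseline measurement". SAP section 9 reports no change: "The statistical methods as described in the protocol were adopted".

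On timing, Protocol 7.1.3 schedules a POC-CCA urine test about 24 hours after dosing, and Protocol 7.1.4 adds another: "At day 8 (+/- 1 day), urine samples will be collected for the POC-CCA test". Kato-Katz is scheduled only before treatment and at D14-D21 (Protocol Appendix II).

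**The concern.** A rule that is harmless for one test has been transferred to another with a different visit schedule. Kato-Katz has no scheduled measurement between the positive baseline and the end of study, so carrying the last value forward and declaring non-response normally give the same answer. POC-CCA has two post-dose tests in between, and either can be negative. LOCF can then turn a missing end-of-study result into a cure, whereas the other sentence, and the protocol, make the same child a failure.

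The endpoint definition does not settle the matter. Protocol 8.3.2 and SAP 6.2 define POC-CCA cure as absence of antigen in urine without naming a day, whereas Kato-Katz cure is tied to 14-21 days after treatment.

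Three things are at stake:
- The reported POC-CCA cure rate would depend on which sentence the programmer follows.
- It would also depend on when children leave the trial.
- In the mITT set a dropout would normally be a failure on Kato-Katz but possibly a cure on POC-CCA, so the two cure rates could differ partly because of imputation.

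**Working it through.** **1. The plan's own figures.** SAP 7.1 and Protocol 8.1 randomise 60 per arm and allow about 17% dropout to keep 50 evaluable. 60 × (1 − 0.17) = 49.8, and 10/60 = 16.7%, so 10 of 60 children without an end-of-study result matches the plan's allowance. The documents give no expected POC-CCA cure rate.

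**2. The rules applied to one child with no D14-D21 result.**

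| Last available result | LOCF | Missing = non-responder (SAP 16.1.1) | Worst case (Protocol 8.5.1) |
|---|---|---|---|
| Kato-Katz: positive baseline | not cured | not cured | not cured |
| POC-CCA: Day 8 positive | not cured | not cured | not cured |
| POC-CCA: Day 8 negative | **cured** | not cured | not cured |
| POC-CCA: Day 8 missing, Day 2 negative | **cured** | not cured | not cured |
| POC-CCA: pre-screening positive only | not cured | not cured | not cured |

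The rules differ only in rows three and four. A Day 2 result is carried forward only if Day 8 is missing as well.

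**3. Size per arm.** Let n = 60 be the children in the arm, m = 10 those without a D14-D21 test, x the observed cures, and q the share of the m whose last post-dose test was negative. Assume that all m had an earlier post-dose test and stay in the mITT set.

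- Worst case: x/n
- LOCF: (x + mq)/n
- Difference: mq/n = 10q/60

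| q (assumed) | Extra cures (10q) | Difference, percentage points |
|---|---|---|
| 0% | 0 | 0 |
| 25% | 2.5 | 4.2 |
| 50% | 5 | 8.3 |
| 75% | 7.5 | 12.5 |
| 100% | 10 | 16.7 |

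The documents give no value for q, so the whole range is shown.

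**4. Illustration with x = 35 observed cures among 50 tested** (an assumed count), with Clopper-Pearson 95% intervals:

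- Worst case: 35/60 = 58.3% (44.9 to 70.9)
- LOCF, q = 50%: 40/60 = 66.7% (53.3 to 78.3)
- LOCF, q = 100%: 45/60 = 75.0% (62.1 to 85.3)

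**5. Effect of one carried-forward negative.** It adds 1/60 = 1.7 points in a Part 1 arm, 1/30 = 3.3 points in C8 and 1/10 = 10 points in C9.

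**6. Analysis sets.** The mITT set (SAP 10.2) keeps randomised children with a baseline, apart from those needing malaria treatment after dosing, so most dropouts remain in it. The PP set drops children whose end-of-study stool is missing or out of window, which removes most of those affected. A missing urine sample is not in the PP exclusion list, so a child with the stool sample but no urine test can stay in PP.

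**The case against.** The strongest reply is that the plan, read sensibly, already gives the right answer. The LOCF sentence in SAP 16.1.1 concerns an egg count. The protocol reserves LOCF for continuous endpoints, POC-CCA cure is binary, and the sentence that transfers naturally is the one about non-responders. SAP section 9 points the same way.

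Much of this stands. A reader might infer that the SAP instructs the analyst to count a child lost after a negative Day 8 test as cured. The documents do not support that, because the non-responder sentence follows directly and gives the opposite result. But the sensible reading is not the only one available. The two sentences can be taken in sequence: impute by LOCF, then treat as non-responders those who still have no value. SAP 16.1.2 repeats LOCF alone for an endpoint that is already binary. Nothing in 16.2.1 chooses between the readings.

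Other points limit the consequences:
- POC-CCA cure is secondary and descriptive, with no hypothesis test. The 70% criterion in Protocol 8.1 is set for the Kato-Katz cure rate, so a reader should not infer that the primary endpoint or that criterion is affected.
- The 17% is a sample-size allowance, not a forecast of losses after Day 8. Some non-evaluable children may leave the mITT set because of malaria treatment.
- Protocol 8.5.1 already plans an observed-case sensitivity analysis, and SAP 16.2.1 displays Day 2 and Day 8 results separately.

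A further inference, that LOCF can never matter for Kato-Katz, is also not established. Protocol 7.1.4 asks for the End of Study procedures at early withdrawal, although 5.5.1 and 5.5.2 say that no further evaluations are done apart from safety. An early post-dose egg count could therefore exist.

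**Conclusion.** The point holds as an unresolved conflict between two inherited rules, one of which contradicts the protocol without being declared as a change. It should be corrected before the POC-CCA cure analysis is programmed.

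The possible shift is 0 to 16.7 percentage points per Part 1 arm, and 8.3 points at an assumed 50% negative. This rests on 10 of 60 children lacking the D14-D21 test, all of them having an earlier post-dose test and remaining in the mITT set, and LOCF being the rule actually programmed. Fewer such children or fewer negative last tests would bring the shift towards zero; if the non-responder sentence is followed, there is none.

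**What to change.** In SAP 16.2.1, state that:
- POC-CCA cure is assessed on the D14-D21 sample only;
- a child in the analysis set without that result is a non-responder, as Protocol 8.5.1 requires;
- Day 2 and Day 8 results are shown descriptively and are not carried forward.

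In SAP 16.1.1 and 16.1.2, remove LOCF for the binary cure endpoint so that the worst-case rule alone applies. Keep LOCF for egg counts in 16.2.2, and keep observed cases as the sensitivity analysis.

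The cost is SAP wording, with no new data collection. The mITT POC-CCA cure rate may come out lower than under LOCF. For Kato-Katz, a child whose only post-dose count comes from an early-withdrawal visit before D14 would count as a non-responder, which follows the protocol rule but could differ from LOCF.

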	• Egg Reduction Rate (ERR, %) calculated based on the arithmetic (and geometric) mean egg count per gram of stool (epg) before and 14-21 days after treatment (as determined by Kato-Katz method).
	• Cure defined as absence of parasite antigens in the urine as assessed by the commercially available POC-CCA test for S. mansoni
	Safety and tolerability endpoints
	• Changes in laboratory safety parameters and vital signs (body temperature, blood pressure and pulse rate)
	• Occurrence, nature, severity and outcome of adverse events
	Occurrence of Adverse Drug Reactions per treatment group
Pharmacokinetics	Originally, a PK profile of L-PZQ, D-PZQ and rac-PZQ (AUC 0-t , $C_{max}$ , $t_{max}$ , $t_{lag}$ , AUC 0-<math>\infty</math> , AUC extra , $t_{\frac{1}{2}}$ , $\lambda_z$ , CL/f and $V_z/F$ ) was to be produced, followed by assessment in 25% of the subjects of cohorts C1-C7 with a rich sampling scheme and in 75% of the subjects with a sparse sampling scheme.
	Further, PK would have been assessed in all subjects of Part 2 (cohorts C8 and C9) with a rich sampling scheme. Due to technical challenges in the preparation of the PK samples, it was decided by the Sponsor that no PK variable calculations will be done. The data will only be listed, and not analysed.
	The planned PK analysis is pending resolution of technical problems with previously validated DBS bioanalytical assay. Depending on the outcome, the PK data may potentially just be listed and not analysed.
Diagnosis	Screening diagnosis of S. mansoni infection will be done using a single POC-CCA urine cassette test. Briefly, one urine sample will be collected from each subject and evaluated with a commercially available POC-CCA cassette test.
	Subjects who are positive for POC-CCA test will provide stool samples to assess infection intensity using the Kato-Katz method.

Subjects will be tested for S. haematobium in order to exclude S. mansoni/S. haematobium co-infections.

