## 10.2.1 Subgroup definition and parameterization

Subgroup analyses will be performed on subgroups as defined below.

The final parameterization will be updated and fixed at the Data Review Meeting at the latest and documented in an amendment to this SAP if different from the following definition.

The following subgroups will be defined:

- Age (some age ranges may not be applicable, depending on certain trial adaptations) Part 1:
  - 2 years  $\leq$  age < 4 years
  - 4 years ≤ age ≤ 6 years (Ref) Part 2:
  - 3 months  $\leq$  age < 13 months
  - 13 months  $\leq$  age < 24 months (Ref)
- Gender
  - Male (Ref)
  - Female
- Severity of infection (as assessed at Pre-screening [D-28 to D-1])
  - S. mansoni infection
    - Light infection: 1 99 eggs per gram of faeces (Ref)
    - $\circ$  Moderate/heavy infection:  $\geq 100$  eggs per gram of feaces
- Treatment group
  - Biltricide® 3x20mg/kg t.i.d
  - Biltricide® 40mg/kg single dose (Ref)
  - rac-PZQ ODT 1x40mg/kg single dose
  - rac-PZQ ODT 1x60mg/kg single dose
  - L-PZQ ODT 1x30mg/kg single dose
  - L-PZQ ODT 1x45mg/kg single dose
  - L-PZQ ODT 1x60mg/kg single dose
- Trial center/country
  - PPD
  - PPD

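### The logistic model for POC-CCA cure inherits egg-count severity from the Kato-Katz analysis and leaves out the child's own baseline POC-CCA grade, so the exploratory Part 1 odds ratios can lose some sensitivity.

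*SAP*

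**What the plan says.** POC-CCA cure is a secondary efficacy endpoint (protocol 8.3.2; SAP 6.2). For its analysis SAP 16.2.1 states: "CR by POC-CCA will be analysed in the same manner as CR by Kato-Katz as described above". The Kato-Katz analysis has two parts.

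- **SAP 16.1.1** gives a proportion cured per cohort with a Clopper-Pearson interval, without covariates and without a test.
- **SAP 16.1.2** adds a supportive model: "Subgroup analysis will be performed utilising logistic regression to model clinical cure", with cure regressed "on gender, age category, severity of infection, day of assessment (e.g., Day 14-21), dose, formulation (ODT or not) and active pharmaceutical ingredient". Odds ratios with 95% Wald intervals and dose-response curves are to be presented.

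SAP 10.2.1 defines severity by stool egg count in two levels, below 100 eggs per gram and 100 or more. SAP 7.2 stratifies the Part 1 randomisation on that factor alone.

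On baseline antigen status, SAP 6.2 says: "Subjects who are positive for POC-CCA test will provide stool samples to assess infection intensity using the Kato-Katz method". By this route the enrolled children start POC-CCA positive. SAP 16.2.1 displays the result as negative, 1+, 2+ or 3+ at pre-screening, Day 2, Day 8 and Day 14 to 21. Baseline grade is therefore recorded and plotted by cohort, but it is not a model covariate, a subgroup or a stratification factor.

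**The concern.** In the Kato-Katz model, severity is the baseline level of the measure that defines cure. When the same covariate list is used for POC-CCA cure, that term becomes the baseline of a different test, and the baseline of the outcome's own test is absent. A child who starts at 3+ has further to fall to become negative than one who starts at 1+, so grade is plausibly prognostic.

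If it is, omitting it from a logistic model has two effects. The conditional dose, formulation and ingredient coefficients shrink towards zero, and any chance difference between arms in starting grade stays in the comparison. The planned plots show how each cohort is spread over the grades at each visit; they do not show cure by starting grade.

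What is at stake is how the exploratory dose-response results for a secondary endpoint are read. Dose-response is a stated secondary objective (protocol 4.2), and protocol 5.2 relies on it in place of exposure-response because PK sampling was stopped. SAP section 5 requires analyses outside the SAP to be labelled as unplanned, so an adjustment added after the grades are seen would carry less weight.

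**Working it through.** **The plan's own figure.** No power or precision is stated for POC-CCA cure. The nearest figure, for Kato-Katz cure, is a probability of around 85% of observing at least 70% cured among 50 children, with 30 light infections at 85% and 20 moderate/heavy at 60%. The true overall rate is 0.6 × 0.85 + 0.4 × 0.60 = 0.75. Summing the two binomials exactly, P(at least 35 of 50) = 84.7%, so the figure reproduces. It says nothing about POC-CCA.

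**Inputs from the documents.** Seven arms of 60 (420 children); severity 60% light and 40% moderate/heavy, that is 36 and 24 per arm; the SAP 16.1.2 covariates. Day of assessment was left out of the simulated model.

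**Assumed inputs.** Conditional dose log odds ratio 0.30 or 0.20 per 10 mg/kg; severity log odds ratio -0.6; cure odds ratio per grade step 1.0, 0.7, 0.5 or 0.35; association between grade and severity none, moderate or strong. Grade enters as two indicator terms. The test is a two-sided 5% Wald test on dose, with 1,500 runs per setting at 0.30 and 4,000 at 0.20.

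**Power for dose, without and with baseline grade** (ranges over the three grade-severity associations)

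| Cure odds ratio per grade step | Dose 0.30: without, with | Dose 0.20: without, with | Gain, points |
|---|---|---|---|
| 1.0 | 90-91%, 90-91% | 59-60%, 59-60% | none |
| 0.7 | 88-90%, 88-91% | 57%, 57-58% | 0-1 |
| 0.5 | 84-86%, 86-88% | 53%, 54-56% | 1-3 |
| 0.35 | 78-81%, 84-87% | 47%, 51-53% | 4-7 |

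**Where the gain comes from.** With a true coefficient of 0.30, the mean estimate without grade is 0.30 at an odds ratio of 0.7, 0.28-0.29 at 0.5 and 0.26-0.28 at 0.35. With grade it is 0.30-0.31 throughout. The standard error does not fall. In a separate run it rose from 0.092 to 0.096 at 0.5 and from 0.093 to 0.101 at 0.35. In variance terms, (0.096/0.092)² = 1.09 and (0.101/0.093)² = 1.18.

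Cross-check at 0.35 with no grade-severity association:

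- Without grade, 0.263/0.093 = 2.83 and Φ(2.83 − 1.96) = 0.81.
- With grade, 0.311/0.101 = 3.08 and Φ(3.08 − 1.96) = 0.87.

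These agree with the simulated 80.5% and 86.8%.

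**Type I error.** With no dose effect, the rejection rate is 4-6% with or without grade.

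**Chance imbalance.** If a third of children are graded 3+, the difference in that share between two arms of 60 has standard deviation √(2 × 1/3 × 2/3 / 60) = 0.086. The simulations give about 8.5-9 points with no grade-severity association and about 7 points with a strong one. Stratifying on egg count therefore removes only part of it.

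**Missing outcomes.** SAP 16.1.1 counts children with missing data as not cured, and SAP 7.1 assumes about 17% dropout. Failures assigned regardless of grade dilute its effect: at 0.35 the gain fell from 5.6 to 4.8 points.

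**The case against.** The strongest reply is that there is no planned power to lose. SAP 7.1 and 16.1.1 rule out hypothesis testing, SAP section 11 calls every test exploratory, and protocol 8.5.3 asks only for a point estimate and interval per arm. Those exact intervals use no covariates, so adding grade would not change them. The dose-selection criterion stated in SAP 7.1 is observed Kato-Katz cure above 70%. All of this stands, and it confines the point to a supportive regression.

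It is also fair that imbalance is partly handled. Severity is both a stratification factor and a covariate, and baseline grade will be visible by cohort. The prognostic value of grade is a plausible argument, not something the documents show.

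A reader might infer a larger loss from the linear-model rule. With a correlation of 0.5 the variance factor is 1 − 0.25 = 0.75, and 80% power becomes Φ(2.80/√0.75 − 1.96) = 90%. That rule does not apply to a binary outcome in a logistic model, where the standard error rises when a prognostic covariate is added. Nor do the documents supply a correlation.

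A reader might also extend the argument to Part 2. It is not randomised and has 30 and 10 infants, so between-arm chance imbalance does not arise there, and extra terms would strain a very small model.

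What survives is the omission itself: the baseline of the outcome's own test is available and unused.

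**Conclusion.** The point holds as a minor, optional improvement to an exploratory Part 1 analysis. The model carried into SAP 16.2.1 adjusts for egg-count severity but not for baseline POC-CCA grade. Its odds ratios can therefore be somewhat attenuated, slightly less sensitive, and open to residual chance imbalance in grade.

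The size depends wholly on how prognostic grade is: negligible at a cure odds ratio of 0.7 per step, small at 0.5, and noticeable only at 0.35. A separate simulation put the gain slightly lower, at about 0 to 1 point for 0.5 to 0.7 and about 5 points at 0.35.

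The documents do not support reading this as a loss of power for the POC-CCA endpoint as a whole, as inflated type I error, or as a flaw in the per-cohort cure rates. The sample size is unaffected. The verdict assumes that the cross-reference in SAP 16.2.1 covers 16.1.2 as well as 16.1.1, which is its natural reading.

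**What to change.** In SAP 16.2.1, state that the Part 1 logistic model for POC-CCA cure uses the SAP 16.1.2 covariates plus baseline POC-CCA grade (1+, 2+, 3+), and that POC-CCA cure is tabulated by baseline grade within cohort. Leave the Part 2 model as it is.

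The cost is one or two extra model terms and one table, all from data already collected. Trial conduct, sample size and the primary endpoint do not change.
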